5. PROTOCOL AMENDMENTS AND UPDATES

None, as this is version 1.0 of the protocol.

6. MILESTONES

Regular study updates will be provided through periodic benefit-risk evaluation reports [PBRERs).

Study milestones are given in the following [table](#).

Table 1 Study Milestones

Milestone	Planned Date
Registration of protocol in the E.U. PAS Register	To be determined
Start of data collection	Q1 2019
End of data collection	October 2028
Study progress reports	According to PBRER schedule
Interim analysis	Annually ^a
Final report of study results	October 2029

E.U. = European Union; PAS = post-authorization study; PBRER = periodic benefit-risk evaluation report

^a Interim analyses will be conducted every year provided that at least 15 new pregnancies have occurred between two interim analyses.

7. RATIONALE AND BACKGROUND

7.1 STUDY RATIONALE

Multiple sclerosis (MS) is a chronic, inflammatory, and demyelinating disease of the central nervous system (CNS) that affects approximately 2.3 million people worldwide ([MSIF 2013](#)). While MS is a global disease, the prevalence of MS is highest in North America and Europe (140 and 108 per 100,000, respectively) ([MSIF 2013](#)). MS is commonly diagnosed during reproductive age, between 20–40 years ([Tullman 2013](#)). Overall, women are affected approximately twice as often as men, except in individuals with the primary progressive multiple sclerosis (PPMS), where there is no gender prevalence difference ([Tullman 2013](#); [MSIF 2013](#)). Reasons for these observed differences are unclear.

In approximately 85% of patients, MS begins as a relapsing, episodic disorder with gradual complete or incomplete recovery (relapsing remitting MS [RRMS]). If left untreated, the majority of these patients will transition to a progressive form characterized by worsening neurologic disability either with or without occasional superimposed relapses (relapsing or non-relapsing secondary progressive MS [SPMS]). Patients accumulate disability as a result of incomplete recovery from acute relapses

and/or gradual disease progression (Tullman 2013). PPMS is a less common form of MS, accounting for approximately 10% of all cases (approximately 40,000 individuals in the United States). It is characterized by a progressive course from disease onset, with infrequent superimposed discrete clinical attacks or relapses (Lublin 2014).

Evidence suggests that inflammation is present in the CNS throughout all MS clinical courses, from RRMS to SPMS and in PPMS (Frischer et al. 2009). Differences between disease phenotypes are due to the differential contribution of each of the inflammatory and neurodegenerative processes to the pathophysiology of CNS damage over time (Frischer et al. 2009; Frischer et al. 2015).

OCREVUS® (ocrelizumab) was approved by the U.S. Food and Drug Administration (FDA) on 28 March 2017, for the treatment of adult patients with relapsing forms of MS (RMS) and PPMS (Genentech Inc. 2017). Subsequently, OCREVUS was approved in the European Union (E.U.) (including Germany), Switzerland, Australia, Canada, and several other countries.

Ocrelizumab is a recombinant humanized monoclonal immunoglobulin G1 (IgG1) antibody that selectively targets CD20-expressing B cells. Two identical, randomized, active-controlled studies (OPERA I [Study WA21092] and OPERA II [Study WA21093]) have demonstrated superior efficacy outcomes versus interferon β -1a in RMS (Hauser et al. 2017); one randomized placebo-controlled study (ORATORIO [Study WA25046]) has demonstrated superior efficacy in PPMS versus placebo (Montalban et al. 2017). Results of these studies show that depletion of CD20+ B cells leads to a significant impact on a broad range of clinical measures of disease, including disability progression, in addition to an impact on magnetic resonance imaging outcomes related to disease progression and reflective of neural tissue loss; thus, further supporting the hypothesis that B cells are central to the pathogenesis of both RMS and PPMS.

Ocrelizumab has demonstrated a favorable safety profile in RMS and PPMS patients (Hauser et al. 2017; Montalban et al. 2017). The proportion of patients with adverse events (AEs) was similar in ocrelizumab patients compared with interferon β -1a (both 83.3%) or placebo patients (95.1% vs. 90.0%). The proportion of patients experiencing a serious adverse event (SAE) was similar between ocrelizumab and the comparator groups (in RMS: 6.9% [ocrelizumab] and 8.7% [interferon β -1a]; in PPMS: 20.4% [ocrelizumab] and 22.2% [placebo]).

7.2 STUDY BACKGROUND

Congenital malformations, structural (e.g., cleft lip/palate, heart defects, neural tube defects, heart defects, abnormal limbs) and functional/developmental (e.g., sensory problems, metabolic disorders, nervous system problems, degenerative disorders), affect about 3.0 per 100 live births in the United States (CDC 2008) and are the leading cause of infant deaths (about 20% of all infant deaths) (Matthews et al. 2015). The

European Surveillance of Congenital Anomalies (EUROCAT) estimated the prevalence of congenital anomalies as 23.9 per 1,000 live births from 2003–2007 (Dolk et al. 2010). It is inconclusive whether MS has an impact on risk of adverse pregnancy and infant outcomes. Some studies suggest there is little evidence that MS increases the risk of adverse pregnancy, delivery, or infant outcomes including perinatal mortality, congenital malformations, and delivery complications (Mueller et al. 2002; Dahl et al. 2005; Houtchens 2007). Other studies suggest pregnancies in women with MS are associated with more frequent operative deliveries, decreased infant birth weight or infants small for gestational age compared with women without MS (Dahl et al. 2005; Dahl et al. 2008; Kelly et al. 2009).

Ocrelizumab is a humanized monoclonal antibody of an IgG1 subtype, and immunoglobulins are known to cross the placental barrier. B-cell levels in human neonates following maternal exposure to ocrelizumab have not been studied in clinical studies. There are no adequate and well-controlled data from studies in pregnant women; however transient peripheral B-cell depletion and lymphocytopenia have been reported in infants born to mothers exposed to other anti-CD20 antibodies during pregnancy (Chakravarty et al. 2011; Klink et al. 2008).

It is not known whether ocrelizumab can affect pregnancy outcomes or infant outcomes in humans. However, based on pathophysiological considerations, ocrelizumab might theoretically affect pregnancy outcomes and infant outcomes in the following ways:

- By direct exposure of the fetus to ocrelizumab, which is assumed to occur after the 16th week of gestation as receptor-mediated transplacental transfer of IgG1; this is minimal during the first trimester of pregnancy (Palmeira et al. 2012; Simister 2003)
- Indirectly due to known or unknown infections or infectious complications in the mother exposed to ocrelizumab during pregnancy, which may affect the offspring, where the infection may be associated with ocrelizumab exposure
- Indirectly due to effects of ocrelizumab on the placenta

Based on the average ocrelizumab terminal half-life of 26 days reported in the studies of MS (Genentech Inc. 2017), it is expected that ocrelizumab would be eliminated from the body approximately 4.5 months after the last administration. Considering the interpatient variability (the longest terminal half-life recorded in women was 53 days) and the absence of placental transfer of immunoglobulins during the first trimester of pregnancy, it is recommended that women of childbearing potential should use contraception while receiving ocrelizumab and for 6 months after the last infusion of ocrelizumab. However, women may get pregnant during this period due to noncompliance with contraception or failure of contraceptive methods.

Clinical studies of the effects on pregnancy and offspring associated with the use of ocrelizumab during pregnancy, during lactation, and/or before conception have not been performed, and experience from ocrelizumab clinical trials is limited. As of 31 January

2017, there were 25 pregnancies reported during ocrelizumab trials in MS. Seven of the 25 pregnancies were electively terminated, and no abnormalities were reported in the embryos or products of conception, one pregnancy ended in stillbirth at approximately 7-8 months of gestation, and there were two live preterm births with abnormal findings (benign nasopharyngeal neoplasm, jaundice, respiratory distress and low birth weight; temperature instability feeding difficulties, bradycardia, respiratory distress, and anemia). Eleven of the 25 pregnancies ended in a live, full-term birth and 4 pregnancies were still ongoing at the time of analysis (Vukusic et al. 2017). In an embryo-fetal development study in cynomolgus monkeys, there was no evidence of teratogenicity or embryotoxicity (Study 04-1272-1342). Also in monkeys, using doses similar to or larger than those used clinically on a mg/kg basis, increased perinatal mortality (in some cases associated with bacterial infections), depletion of circulating B cells, and toxicity to kidneys (glomerulopathy and inflammation), bone marrow (lymphoid follicle formation), and testis (reduced weight) were seen in the offspring in the absence of toxicity in the mother (Genentech Inc. 2017). Transient peripheral B-cell depletion and lymphocytopenia have been reported in infants of women treated during pregnancy with other drugs with the same mechanism of action. Due to the potential depletion of B-cells in neonates and infants of mothers who have been exposed to OCREVUS during pregnancy, it is recommended that vaccination with live or live-attenuated vaccines should be delayed until B-cell levels have recovered; therefore, measuring CD19-positive B-cell level, in neonates and infants, prior to vaccination is recommended. It is recommended that all vaccinations other than live or live-attenuated should follow the local immunization schedule. Measurement of vaccine-induced response titers should be considered to check whether individuals can mount a protective immune response, because the efficacy of the vaccination may be decreased (study BN29739, unpublished results). Ocrelizumab was excreted in the milk of treated monkeys. The effects on the infant of ocrelizumab exposure through lactation are not known (Genentech Inc. 2017).

The Ocrelizumab Pregnancy Registry will be conducted to fulfill part of the FDA postmarketing requirements (PMR) (3194-3) for approval of ocrelizumab in the United States.

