9.3.2.2.11 Adverse Infant and Childhood Outcomes Related to Immune Suppression

Adverse infant and childhood outcomes related to immune suppression include neutropenia, lymphopenia, leukopenia, decreased B-cell counts, hypogammaglobulinemia, inadequate vaccine response, and events related to a potential immune mediated mechanism, including thrombocytopenia.

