9.4.2 Data Collected during the Observation Period

After a patient provides consent, the CC will obtain demographic and contact information in addition to baseline information at the time of enrollment. All patient and HCP contact information will be confidential and will remain at the CC. The CC will then contact the patient each trimester to update contact information and ascertain the occurrence of pregnancy outcomes or other events (see [Section 9.3](#) for list of variables). Below is a list of the expected contacts with patients and HCPs:

Expected contacts with patient:

- Enrollment
- End of Trimester 1 (approximately 14 gestational weeks)
- Mid-Trimester 2 (approximately 21 gestational weeks)
- Mid-Trimester 3 (approximately 34 gestational weeks)
- EDD plus 4 weeks
- Birth plus 12 weeks, 26 weeks, and 52 weeks (live births only)

Expected contacts with the patient's HCP (neurologist, obstetrician):

- Enrollment
- Mid-Trimester 2 (approximately 21 gestational weeks)
- EDD plus 4 weeks

Expected contacts with the infant's HCP (live births only):

- EDD plus 4 weeks
- Birth plus 12 weeks
- Birth plus 26 weeks
- Birth plus 52 weeks

[figure not shown]
After a patient is enrolled, there will be at least three attempts made to contact the patient and/or the HCP via phone, e-mail, fax, and mail, as appropriate, approximately 10 business days apart. If data is obtained after a follow-up interval is passed, the CC will accept and enter the data and continue follow-up of the patient. If an HCP is not responsive at the time points described above, the patient will be asked to provide the information contained on the HCP worksheets. If the HCP then responds to contact, their information will supersede the patient-reported information. At all time points, the type of reporter (patient, obstetrician, neurologist, or infant HCP) will be recorded.

In the routine care setting, patients are seen regularly by their treating physicians either for treatment or for regular assessment after treatment. Thus, no study-specific visits or evaluations are required by this protocol.

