9.7 DATA ANALYSIS

Descriptive statistics will be used to summarize the findings; specifically, overall frequency (prevalence, 95% CI) of selected adverse pregnancy outcomes will be calculated, as well as frequencies of specific outcomes, e.g., major congenital malformations (primary outcomes); spontaneous abortions, stillbirths, elective or therapeutic terminations, and preterm births (secondary outcomes). Prevalence and associated 95% CIs will also be calculated for selected adverse fetal, neonatal, and infant outcomes at birth and through at least the first year of life of infants from pregnancies in women with MS exposed to ocrelizumab (i.e., major and minor congenital malformations, small for gestational age, postnatal growth and development, and outcomes related to immune suppression. Similar descriptive analyses summarized above will be performed on the internal comparator group consisting of pregnant women with MS who were not exposed to any MS DMTs (apart from glatiramer acetate). Outcomes will be compared with the internal comparator group and other available

background prevalence from external comparator populations. See Methods of Analysis [Section 9.7.1](#) for additional details.

The comparison to ocrelizumab-exposed women to the internal comparator will be performed using risk ratios (95% CIs) unadjusted and adjusted to relevant covariates, if sufficient number of outcomes are available. See Comparative Analysis [Section 9.7.2](#) for additional details.

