9.7.2.1 Internal Comparator Group

The internal comparator group will consist of pregnant women with MS who are unexposed to DMTs, apart from glatiramer acetate (See [Section 9.2.2.2](#)). Identical data collection and follow-up procedures will be used for the ocrelizumab-exposed pregnant women and unexposed pregnant women with MS. Covariates collected in both exposed and unexposed groups include the following: pregnancy follow-up and frequency of mother and infant encounters, medical and medication history, MS disease history and relapses during follow-up, and pregnancy and infant outcomes (see [Appendix 2](#) and [3](#)). This comparator study population will be recruited from the same clinical centers as the ocrelizumab-exposed pregnant women, in both the United States and other countries.

There is sufficient clinical evidence to allow pregnant women with MS who are exposed to glatiramer acetate early in pregnancy to enroll in the internal comparator. Since FDA drug approval in 1996, studies of glatiramer acetate have not shown to increase the risk of adverse pregnancy or delivery outcomes compared to women unexposed to DMTs during pregnancy ([Copaxone \[Teva\] Prescribing Information](#); [Fragoso 2014](#); [Sandberg-Wollheim et al. 2018](#)), including in the first trimester ([Herbstritt et al. 2016](#)); thus, exposure to this particular MS DMT will be permitted as part of the ocrelizumab-unexposed group to increase the feasibility to recruit an internal comparator group from the same sites. However, analyses stratification based on glatiramer acetate exposure will also be performed.

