Appendix 2 Data Collection Overview (as per Standard of Care)

Data Collection ^a	Enrollment	Prenatal Follow-Up			Pregnancy Outcome	Pediatric Follow-Up	Early Termination of Study Participation Contact
		End 1st Trimester (~14 weeks)	Mid 2nd Trimester (~21 weeks)	Mid 3rd Trimester (~34 weeks)	~4 weeks after EDD	Infant Age 12, 26, and 52 Weeks	End of Patient Participation in Study
Informed consent ^b	x						
Inclusion/exclusion criteria	x						
Patient demographics and characteristics	x						
Medical history	x						
MS disease and treatment history	x						
Pregnancy history, and current pregnancy information ^c	x						
Lifestyle factors ^d	x	x	x	x	x		
Prior and concomitant medications ^e	x	x	x	x	x		
Ocrelizumab treatment ^f	x	x	x	x	x		x
Comorbid conditions	x	x	x	x	x		
MS disease status ^g		x	x	x	x		
Current pregnancy status		x	x	x			x ^h
Gestational age (weeks)		x	x	x	x		x ^h
Pregnancy outcome ⁱ					x		x ^h
Infant characteristics					x ^j	x ^k	x ^h
Infant abnormalities ^l					x	x	x ^h
SAEs related to pregnancy,	x	x	x	x	x	x	x ^h

Data Collection ^a	Enrollment	Prenatal Follow-Up			Pregnancy Outcome	Pediatric Follow-Up	Early Termination of Study Participation Contact
		End 1st Trimester (~14 weeks)	Mid 2nd Trimester (~21 weeks)	Mid 3rd Trimester (~34 weeks)	~4 weeks after EDD	Infant Age 12, 26, and 52 Weeks	End of Patient Participation in Study
pregnancy outcome, or infant SAEs and severe infections (NCI CTCAE Grade 3) in infants ^m							
Reason for early termination of study participation							x

EDD = expected date of delivery; EDSS = Expanded Disability Status Scale; LMP = last menstrual period; MS = multiple sclerosis; SAE = serious adverse event; NCI CTCAE = National Cancer Institute Common Terminology Criteria for Adverse Events

- ^a Available data will be collected; no additional diagnostic or monitoring procedures shall be applied to the patients outside of routine clinical practice.
- ^b Written or verbal informed consent must be obtained before any data collection (per local regulations or ethics committee requirements). If the patient is a minor, written consent must be obtained from the parent or legal guardian.
- ^c Including previous pregnancy outcomes, detailed family history including pregnancy complications, adverse pregnancy outcomes and developmental abnormalities, and information about baseline risks.
- ^d Including smoking, use of caffeine, use of alcohol, and use of recreational drugs.

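### A recommendation to test B cells applies to exposed infants but not comparators, so the internal comparison of B-cell and vaccine-response outcomes mixes drug effect with differences in testing

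*Protocol*

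**What the plan says.** Section 7.2 of the protocol gives the reason for infant testing as follows: "Due to the potential depletion of B-cells in neonates and infants of mothers who have been exposed to OCREVUS during pregnancy". It delays live vaccines until B cells have recovered and adds that "measuring CD19-positive B-cell level, in neonates and infants, prior to vaccination is recommended". On vaccine response it says: "Measurement of vaccine-induced response titers should be considered to check whether individuals can mount a protective immune response". Neither test depends on symptoms. The protocol contains no counterpart for infants in the internal comparator group.

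The registry itself orders nothing. Section 9.4.2 states that "no study-specific visits or evaluations are required by this protocol", and Appendix 2 that "no additional diagnostic or monitoring procedures shall be applied to the patients outside of routine clinical practice". Infant laboratory values are taken where they exist (9.3.2.3). Tables 3, 4 and 5 of Appendix 3 attach two items to them, the date and the result.

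Section 9.3.2.2.11 makes a secondary outcome of immune-suppression events: "neutropenia, lymphopenia, leukopenia, decreased B-cell counts, hypogammaglobulinemia, inadequate vaccine response", and thrombocytopenia. Under Appendix 4.3.3, a suggestive infant laboratory result is recorded whether or not it is serious or accompanied by symptoms.

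Section 8.2 includes a comparison of infant outcomes with women with MS not exposed to ocrelizumab. Section 9.7 lists immune-suppression outcomes among those to be summarised and then says: "Outcomes will be compared with the internal comparator group". Risk ratios against that group are planned if events are numerous enough. Section 9.7.2.1 says: "Identical data collection and follow-up procedures will be used for the ocrelizumab-exposed pregnant women and unexposed pregnant women with MS".

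**The concern.** A silent laboratory abnormality becomes an event only if somebody tests. One group has a written recommendation to screen and the other has not. Identical forms and contact schedules do not make the testing alike. Screened exposed infants would include healthy ones, whereas comparator infants may be tested mainly when there is a clinical reason.

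A ratio over all live births then depends on how many infants were tested in each group. A ratio among tested infants depends on why they were tested. B-cell depletion is the mechanistic concern that section 7.2 raises for these infants, so a distorted contrast could either raise a false alarm or conceal a real effect. Because the reason for testing is not among the listed data elements, the two sources of difference could not be separated properly afterwards.

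**Working it through.** **Plan's own figure.** There is none for this point. The protocol gives no share of infants tested and no planned effect size for immune outcomes. Its 290 enrolled and 153 outcomes (290 × 0.85 × 0.62 = 152.8) were derived for major congenital malformations.

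**Inputs.** All of the following are assumptions for illustration:
- true prevalence q = 5% in both groups, so the true risk ratio is 1;
- tested shares tE (exposed) and tC (comparator);
- abnormal shares among tested infants, aE and aC;
- exposed infants screened regardless of illness, so aE = q = 5%.

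**Formulas.**
- All live births: RR = (tE × aE) / (tC × aC)
- Tested infants only: RR = aE / aC

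**All live births.**

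| Tested, exposed v comparator | Comparator testing | Detected, exposed | Detected, comparator | Apparent RR |
|---|---|---|---|---|
| 60% v 10% | unrelated to illness, aC = 5% | 0.60 × 5% = 3.0% | 0.10 × 5% = 0.5% | 6 |
| 60% v 10% | for cause, aC = 20% | 3.0% | 0.10 × 20% = 2.0% | 1.5 |
| 30% v 20% | for cause, aC = 20% | 0.30 × 5% = 1.5% | 0.20 × 20% = 4.0% | 0.375 |

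The for-cause rows are feasible. With 10% tested, the 2.0% detected is 40% of the 5% affected. The remaining tests fall on 8.0/95 = 8.4% of unaffected infants, so affected infants are about 4.75 times as likely to be tested (40/8.4). The 30% v 20% row implies the same ratio (80% against 16.8%).

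The all-birth ratio equals (tE/tC) × (aE/aC). With aE/aC = 5/20, it crosses 1 when exposed infants are tested four times as often as comparators.

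**Tested infants only.** With 5% v 20%, RR = 0.25. More generally, if affected comparator infants are k times as likely to be tested, aC = kq / (kq + 1 − q):

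| k | q = 5%: aC, apparent RR | q = 10%: aC, apparent RR |
|---|---|---|
| 2 | 9.5%, 0.53 | 18.2%, 0.55 |
| 3 | 13.6%, 0.37 | 25.0%, 0.40 |
| 5 | 20.8%, 0.24 | 35.7%, 0.28 |

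A true risk ratio of 2 doubles each entry, to between 0.48 and 1.10. A real doubling could therefore look like no effect or like protection.

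**Counts.** Take about 153 live births per group, assuming the same drop-out and live-birth rates for comparators. At 60% v 10% tested, 153 × 3.0% = 4.6 exposed events would be seen, against 153 × 0.5% = 0.8 or 153 × 2.0% = 3.1 comparator events, with no drug effect in either case.

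**The case against.** *Scope.* Section 7.2 names CD19 and, more weakly, vaccine titers. It says nothing about neutrophils, immunoglobulins or platelets. A reader might infer that every laboratory-defined immune outcome is affected. The documents do not show that; other counts might be measured at the same time, but this is not stated. The recommendation also concerns exposure during pregnancy, while the exposed group includes women exposed only in the six months before the last menstrual period. Testing may therefore differ within that group, and its uptake is unknown. All of this stands and limits the point.

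*Size.* A reader might infer that the all-birth ratio is inflated by the ratio of tested shares, so that 60% v 10% must give 6. That requires testing unrelated to illness. It conflicts with the other half of the argument, in which comparators are tested for cause. Nor does the denominator alone fix the direction: at 30% v 20% both denominators give ratios below 1.

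*SAP territory.* Section 9.7.2 opens by naming only malformation, spontaneous abortion and preterm birth rates. Risk ratios are conditional on numbers, and full details go to the SAP. That is fair as to method. Sections 8.2 and 9.7 nevertheless cover infant outcomes generally, and no choice of denominator supplies a reason for testing that was never collected.

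*Partly handled.* Dates of laboratory tests, vaccinations and infant serious adverse events are collected, so some pre-vaccination tests and some tests around serious illness could be recognised. Tests prompted by minor illness could not. Section 9.7.2.1 is accurate about procedures and does not claim equal testing.

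**Conclusion.** The point holds for decreased B-cell counts and inadequate vaccine response, and possibly for other laboratory-defined immune outcomes if they are measured alongside. As planned, the internal comparison of these outcomes cannot separate drug effect from differences in who was tested and why.

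Size and direction are unknown because the protocol gives no testing rates. Under the illustrative assumptions, with a true ratio of 1, the all-birth ratio lies anywhere from about 0.4 to 6. Among tested infants the ratio falls below the truth whenever comparators are tested for cause and exposed infants are screened regardless of illness: 0.25 in the main example, 0.24 to 0.55 across the range tried.

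A reader might conclude that no between-group ratio should be given for any laboratory outcome. The text does not support going that far: the written asymmetry covers two measurements, and routine tests could be compared if enough comparator infants have them. Section 9.9 discusses early losses, loss to follow-up, recall and channeling, but not differential testing. The correction is cheap and worth making.

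**What to change.** - **Appendix 3, Tables 3 to 5:** add a *reason for test* item to the infant laboratory row, with the options routine/pre-vaccination or clinical indication. This asks for no additional test.
- **Sections 9.7 and 9.7.2:** report the number of infants tested by group and by reason. Present CD19 and vaccine-response results descriptively among tested infants. Give a between-group risk ratio for them only for routine tests, and only if enough comparator infants have such tests.
- **Keep the risk ratios** for serious or Grade 3 and higher infections, hospitalisation and death. These depend less on elective testing, although the protocol does not show that they are ascertained identically.
- **Section 9.9:** add differential testing to the limitations.

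The cost is one extra eCRF field and some analysis wording. Appendix 3 already says its variables may change. The loss is an overall between-group ratio for CD19 and vaccine response.
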